2.3.2 Additional analysis

An additional evaluation of the primary endpoint will be made, including actual concizumab dose level (interpreted as the patient's last dose level) as additional factor in the primary analysis model specified above. Point estimates and 95% confidence interval will be provided for the ABR at the different dose levels of concizumab (0.15, 0.20 and 0.25 mg/kg). Furthermore, a series of analyses with individual steady state PK/PD assessments included as log-transformed covariates in the negative binomial regression model as specified for the primary analysis will be performed in order to evaluate possible associations between PK/PD and ABR that potentially could guide dose-selection. The referred steady-state PK/PD assessments comprise the concizumab trough level, maximum plasma concentration (C_{\max}) of concizumab, TFPI value prior to the last s.c. dose

Statistical Analysis Plan
 Trial ID: NN7415-4255
 UTN: U1111-1179-3872
 EudraCT No.: 2016-000614-29

~~CONFIDENTIAL~~

Date: 13 July 2018
 Version: 1.0
 Status: Final
 Page: 9 of 14

Novo Nordisk

administration, peak thrombin generation (nM), Endogenous thrombin potential (nM*min) and velocity index (nM/min) prior to the last dose administration at 24 weeks.

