1.1 Trial information

NN7415-4255, explorerTM5, multi-centre single arm trial, which aim to evaluate the efficacy and safety of concizumab 0.15 mg/kg (with potential dose escalation) administered daily s.c. in patients with severe haemophilia A without inhibitors. For further information about the trial please refer to the protocol.

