Two criteria will be evaluated in a hierarchical fashion in support of CPoC comprising a comparison of the ABR of all patients with a threshold of 12, irrespective of individual dose titration. The primary CPoC criterion aims at evaluating the effect of concizumab at the last dose level reached for a patient. Hence, for this evaluation, only observations from the period where patients are on their end dose at time of analysis will contribute to the analysis. Furthermore, observations from the 2 week run-in period will be not be included. Since this evaluation disregards a subset of data collected the result should be viewed taking in to account the potential bias. The second CPoC criterion aims at evaluating the effect of concizumab when given as an escalation regimen. Hence, this will compare the ABR of haemophilia A patients treated with concizumab with the typical historical ABR of haemophilia A patients being treated on-demand using all data after enrolment. The second CPoC criterion will only be evaluated if the first one succeeds.

The referred comparisons will be made using a negative binomial model with log of exposure time in main part as offset. For each criterion, evidence of effect will be concluded if the 95% confidence interval of the estimated ABR is below 12.

Clinical arguments for the hierarchical test approach

Concizumab exhibits non-linear PK due to target mediated drug disposition and it is expected that the dose response curve of the ABR is rather steep. This implies that patients that are on a dose which is not efficacious are likely to bleed as patients that are not treated at all. Subset of data collected from the last dose clinically deemed as efficacious would reflect the efficacy of concizumab in the given patient.

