2.5 Interim analysis

The trial does not include a formal interim analysis. However, the split of the trial into a main and extension part offers the opportunity of reporting results before the end of the trial. Other reporting of the trial might be done during the extension part once the data collection and review of the main part data has been finalised and individual clinical study reports might in such case be issued. A final clinical study report describing results from the main and extension part will be written when the last patient has either completed or withdrawn from the trial.

All main conclusions regarding clinical proof of concept and dose guidance for phase 3 will be based on the reporting after the main part, see [Figure 2-1](#).

[figure not shown]

Figure 2-1 Definition of main and extension part

Statistical Analysis Plan
Trial ID: NN7415-4255
UTN: U1111-1179-3872
EudraCT No.: 2016-000614-29

~~CONFIDENTIAL~~

Date: 13 July 2018
Version: 1.0
Status: Final
Page: 13 of 14

Novo Nordisk

3 Changes to the statistical analyses planned in the protocol

As described in section 1.2 of this document, the scope of this SAP is to specify some further technical details on matters which have not been adequately described in the protocol. No changes have been made to the analyses specified in the protocol.

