3.5 Clarification of additional analyses

Section 17.5 of the protocol describes the additional analyses of the primary endpoint. Section 2.3.2 of this document clarifies how the additional analysis including actual concizumab dose level as factor in the primary analysis model should be interpreted as including the patient's last dose level as factor in the primary analysis.

Further, section 2.3.2 of this document clarifies that a series of additional analyses will be performed with each of the PK/PD variables taken prior to last dose at 24 weeks. Each of these PK/PD variables will be included as log-transformed covariates in the negative binomial regression model.

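### ABR by last dose level describes patient groups selected by response, so it is biased as an estimate of ABR at each dose and can flatten or reverse the dose-response

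*SAP*

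**What the plan says.** Section 1.1 describes a "multi-centre single arm trial, which aim to evaluate the efficacy and safety of concizumab 0.15 mg/kg (with potential dose escalation", so dose is not randomised. Section 2.3.2 plans a further evaluation of the primary endpoint "including actual concizumab dose level (interpreted as the patient's last dose level) as additional factor in the primary analysis model specified above", reported as follows: "Point estimates and 95% confidence interval will be provided for the ABR at the different dose levels of concizumab (0.15, 0.20 and 0.25 mg/kg". Section 3.5 repeats that the factor "should be interpreted as including the patient's last dose level as factor in the primary analysis".

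Sections 2.3 and 3.2 define two offsets: time on the last dose level without run-in (first CPoC criterion), and all time in the main part (second criterion). Section 2.3.2 refers back to the primary model without choosing between them.

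On how a patient arrives at the last dose, Section 2 (clinical arguments for the hierarchical approach) says that "patients that are on a dose which is not efficacious are likely to bleed as patients that are not treated at all" and that "Subset of data collected from the last dose clinically deemed as efficacious would reflect the efficacy of concizumab in the given patient". It also expects a steep dose-response.

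On use, Section 2.5 says "All main conclusions regarding clinical proof of concept and dose guidance for phase 3 will be based on the reporting after the main part".

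**The concern.** If patients move up because they bleed, the last dose is a consequence of the outcome being modelled. Those still at 0.15 mg/kg are then selected for bleeding little, and those at the top level for bleeding often. A between-patient factor for last dose compares these groups, not the doses. The result carries a dose label and a confidence interval, and it is the only planned estimate of ABR by dose. Nothing in Sections 2.3.2 or 3.5 mentions the selection, adjusts for it or limits the interpretation. At stake is what the main-part report says about dose before phase 3.

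**Working it through.** **1. The plan's own figures.** Section 2.1 assumes 30 patients, ABR 4, 6 months and over-dispersion 6 (read as variance/mean), and states about 95% power against 12. A Wald formula on log ABR gives Φ(ln(12/4)/√(6/(30 × 4 × 0.5)) − 1.96) = Φ(1.099/0.316 − 1.96) = Φ(1.51) = 93.5%. Simulating the negative binomial fit gives 96.0%. The stated figure is reproduced, and this calculation does not involve the dose factor.

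The same section implies more bleeding in the time that the first criterion leaves out:
- all main-part data: 5.4 × 8/12 = 3.6 bleeds per patient;
- end dose only: 4 × 6/12 = 2.0 bleeds;
- difference: 1.6 bleeds in 2 months, an ABR of 1.6 × 12/2 = 9.6, against 4 at end dose.

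This fits escalation that follows bleeding but does not prove it.

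**2. Simulation inputs.** From the SAP: 36 patients, start at 0.15 mg/kg, three levels. Assumed: 32 weeks of follow-up; true ABR 6 at 0.15; one level up after 3 bleeds in 12 weeks; persistent gamma-distributed patient rates. Shape 0.4 follows from Section 2.1: mean 2 bleeds, 2/(6 − 1) = 0.4. Shape 2.0 is a milder alternative. There were 400 trials per scenario. ABR by last dose is bleeds divided by time in each group. The last column is the share of trials in which escalated patients had the higher ABR, on last-dose time.

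| True ABR 0.15 / 0.20 / 0.25 | Patient variation | Last-dose time | Whole main part | Escalated higher |
|---|---|---|---|---|
| 6 / 6 / 6 | shape 0.4 | 1.3 / 4.8 / 24.3 | 1.3 / 7.8 / 22.0 | about 100% |
| 6 / 4.2 / 3 | shape 0.4 | 1.3 / 4.0 / 13.6 | 1.3 / 7.4 / 16.3 | about 100% |
| 6 / 3 / 1.5 | shape 0.4 | 1.3 / 3.5 / 7.6 | 1.3 / 7.2 / 13.2 | about 100% |
| 6 / 4.2 / 3 | shape 2.0 | 2.6 / 3.8 / 6.9 | 2.6 / 7.3 / 12.5 | 94% |
| 6 / 4.2 / 3 | no persistent differences, bleeds cluster in time | 1.3 / 1.3 / 2.9 | 1.3 / 11.2 / 20.2 | 52% |
| 6 / 4.2 / 3 | escalation unrelated to bleeding | 6.0 / 4.2 / 2.7 | 6.0 / 5.0 / 3.9 | 26% |

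At shape 0.4, triggers of 2 and 4 bleeds also gave about 100%. The last row isolates the cause: once escalation no longer follows bleeding, last-dose time returns the right order, and 26% is chance.

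**3. Steep dose effect.** Separate runs used 24 to 46 weeks of follow-up and a true ABR of 12 / 4 / 1. With dispersion 0.83 and a trigger of 3, the result was 2.4 / 3.0 / 2.5, with the top level above the bottom in 52% of trials. A trigger of 5 gave 27%. With dispersion 0.2 and a trigger of 3, it was 3.8 / 3.0 / 1.4, reversed in 6%. The 0.15 level was still only 2.4/12 = 20% to 3.8/12 = 32% of its true value.

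**4. Either offset.** Last-dose time drops the bleeds that led to escalation. The whole main part charges them to the higher dose. The table shows bias both ways, and the last row shows that the whole-main-part offset mixes doses even when escalation is unrelated to bleeding.

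**5. A within-patient alternative.** A model over all dose periods, with time-varying dose and a gamma patient effect, was run at shape 0.4 with a trigger of 3. It gave median rate ratios of 1.08 and 1.05 (truth 1 and 1), and 0.76 and 0.54 (truth 0.7 and 0.5). Where bleeding clustered only over time within a patient, it gave 0.16 and 0.07 (truth 1 and 1), a large spurious benefit.

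**The case against.** The strongest reply is that the escalation rule is not in the SAP. That it follows bleeding is inferred from Section 2, and every magnitude above rests on that. This stands as a condition: if escalation were unrelated to bleeding, the systematic distortion on last-dose time would vanish.

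A reader might infer that the lowest level must look best and the highest worst. The documents do not support this. Section 2 expects a steep dose-response, and with a steep effect reversal ranged from 6% to 52% of trials. What remains is the level bias at 0.15 mg/kg.

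A reader might also infer that these ABRs select the phase 3 dose. In Section 2.3.2 the remark about guiding dose selection belongs to the PK/PD covariate analyses. The link to the by-dose ABRs runs only through Section 2.5, which refers to the main-part reporting as a whole. No test or decision rule is attached to them.

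Nor does the SAP establish that the triggering bleeds are dropped: that is one of two readings of the offset.

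Finally, Section 2 does carry a warning: "Since this evaluation disregards a subset of data collected the result should be viewed taking in to account the potential bias". It concerns data left out of the primary CPoC criterion, not selection into dose groups, and it is not carried into Section 2.3.2.

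**Conclusion.** The point holds, conditional on escalation following bleeding. ABR by last dose then describes response-selected groups. It is biased as an estimate of ABR at each dose, with the 0.15 mg/kg level too low (1.3 to 2.6 against a true 6; 2.4 to 3.8 against a true 12), and it can flatten or reverse the dose-response under either offset. How far depends on three things the SAP does not settle: how much patients differ persistently, how steep the dose effect is, and the escalation rule.

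The CPoC comparisons with 12 contain no dose factor, so they and their power are unaffected by this point. The analysis is additional and not confirmatory, so the harm is confined to dose guidance. Severity: should-fix.

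**What to change.** 1. In Section 2.3.2, and correspondingly in 3.5, state that ABR by last dose level is descriptive of groups selected by response and will not support dose-response or dose-guidance conclusions. State which of the two offsets applies. Confirm from the protocol what drives escalation. No change to dosing or escalation is suggested.
2. Add a sensitivity analysis with one record per patient per dose level, log time on that level as offset, dose as a time-varying factor and a patient random effect. Use all data that could have driven escalation. Include run-in time or handle it explicitly: dropping it may remove bleeds that led to escalation, while Section 2.3.1 notes that some patients stayed on earlier prophylaxis then.
3. State that model's assumptions: differences between patients persist over time, and escalation depends only on the modelled bleeds. The second is doubtful if untreated bleeds, re-bleeds (neither is counted in the endpoint) or clinical judgement play a part. State also that it can show a spurious dose benefit if bleeding clusters over time within a patient. For this reason it should accompany the descriptive table and not be presented as a full remedy.

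Cost: SAP wording and one extra model on data already collected. Intervals will be wide at levels few patients reach (in the 6 / 4.2 / 3, shape 0.4 scenario, on average 25.0, 5.4 and 5.6 patients ended at the three levels), and the estimates rely on the assumed frailty distribution.

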2.4 Supportive secondary endpoints

2.4.1 Supportive secondary efficacy endpoints

- The number of bleeding episodes during 76 weeks from treatment onset
- The number of spontaneous bleeding episodes during at least 24 weeks from treatment onset
- The number of spontaneous bleeding episodes during 76 weeks from treatment onset

The supportive secondary endpoints will be analysed using the same two analyses as for the primary endpoint; one only including observations from the period on the last dose level and one including the entire escalation regimen.

2.4.2 Supportive secondary safety endpoints

- Number of treatment-emergent adverse events (TEAEs) during at least 24 weeks from treatment onset
- Number of TEAEs during 76 weeks from treatment onset.
- Occurrence of anti-concizumab antibodies during at least 24 weeks from treatment onset.
- Occurrence of anti-concizumab antibodies during 76 weeks from treatment onset.
- Change from baseline of fibrinogen during 24 weeks from treatment onset.
- Change from baseline of fibrinogen during 76 weeks from treatment onset.
- Change from baseline of D-dimer during 24 weeks from treatment onset.
- Change from baseline of D-dimer during 76 weeks from treatment onset
- Change from baseline of prothrombin fragment 1 + 2 (F1 + 2) during 24 weeks from treatment onset.
- Change from baseline of F1 + 2 during 76 weeks from treatment onset.
- Change from baseline of prothrombin time (PT) during 24 weeks from treatment onset.
- Change from baseline of PT during 76 weeks from treatment onset.
- Change from baseline of activated partial thromboplastin time (APTT) during 24 weeks from treatment onset.
- Change from baseline of APTT during 76 weeks from treatment onset.
- Change from baseline of antithrombin (AT) during 24 weeks from treatment onset.
- Change from baseline of AT 76 weeks from treatment onset.

Adverse Events will be coded using the most recent version of Medical Dictionary for Regulatory Activities (MedDRA) coding.

Statistical Analysis Plan
 Trial ID: NN7415-4255
 UTN: U1111-1179-3872
 EudraCT No.: 2016-000614-29

~~CONFIDENTIAL~~

Date:	13 July 2018	Novo Nordisk
Version:	1.0	
Status:	Final	
Page:	10 of 14	

A Treatment Emergent Adverse Event (TEAE) is defined as an event that has onset from the first exposure to treatment until the last visit in the trial. Treatment-emergent adverse event endpoints will be summarised by system organ class, preferred term, seriousness, severity and relation to trial product. All Adverse events will further be listed. Relations to Novo Nordisk products used by patients in the trial, such as turoctocog alfa/NovoEight[®], is reported as described in section 12.2 of the protocol and will be transferred to the Argus safety system and not reported in the report of the trial.

Frequency of binding anti-concizumab antibodies will be listed and summarised by time frame according to the two endpoint definitions.

All laboratory safety endpoints will be plotted by time, both as absolute values and change from baseline. Laboratory safety endpoints will further be summarised and listed.

2.4.3 Supportive secondary pharmacokinetic endpoints

- Concentration of concizumab prior to the last dose administration at 24 weeks
- Concentration of concizumab prior to the last dose administration at 76 weeks

The pharmacokinetic endpoints will be summarised and listed.

2.4.4 Supportive secondary pharmacodynamic endpoints

- *Free TFPI concentration*
 - Value prior to the last dose administration at 24 weeks
 - Value prior to the last dose administration at 76 weeks
- *Thrombin generation*
 - Peak thrombin generation (nM) prior to the last dose administration at 24 weeks
 - Peak thrombin generation (nM) prior to the last dose administration at 76 weeks
 - Endogenous thrombin potential (nM*min) prior to the last dose administration at 24 weeks
 - Endogenous thrombin potential (nM*min) prior to the last dose administration at 76 weeks
 - Velocity index (nM/min) prior to the last dose administration at 24 weeks
 - Velocity index (nM/min) prior to the last dose administration at 76 weeks

The PD endpoints will be summarized and listed.

Statistical Analysis Plan
 Trial ID: NN7415-4255
 UTN: U1111-1179-3872
 EudraCT No.: 2016-000614-29

~~CONFIDENTIAL~~

Date: 13 July 2018
 Version: 1.0
 Status: Final
 Page: 11 of 14

Novo Nordisk

2.4.5 Exploratory endpoints

2.4.5.1 Exploratory safety endpoints

- Number of adverse events related to technical complaints during at least 24 weeks from treatment onset
- Number of adverse events related to technical complaints during at least 76 weeks from treatment onset

Adverse events related to technical complaints will be listed and summarised

2.4.5.2 Exploratory patient reported outcome endpoints

- Change in Hemo-TEM after 24 weeks from treatment onset
- Change in Hemo-TEM after 76 weeks from treatment onset
- Change in SF-36v2 after 24 weeks from treatment onset
- Change in SF-36v2 after 76 weeks from treatment onset
- Change in SDS after 24 weeks from treatment onset
- Change in SDS after 76 weeks from treatment onset
- Change in TSQM after 24 weeks from treatment onset
- Change in TSQM after 76 weeks from treatment onset
- Change in SIAQ-ISRQ after 24 weeks from treatment onset
- Change in SIAQ-ISRQ after 76 weeks from treatment onset
- Status of PGI-C after 24 weeks from treatment onset

Patient reported outcomes (PROs) will be collected using questionnaires at visits 1, 2, 4, 5, 6, 7, 8, 9, 10 and 16.

Patient reported outcome questionnaires to be analysed:

- Haemophilia Treatment Experience Measure (Hemo-TEM)
- Validated Hemophilia Regimen Treatment Adherence Scale – Prophylaxis (VERITAS-Pro[®]) or Validated Hemophilia Regimen Treatment Scale (/ VERITAS-PRN[®])
- 36-Item Short Form Health Survey (SF-36v2) (4 week recall)
- Patient Global Impression of Change (PGI-C)
- Sheehan Disability Scale (SDS)
- Treatment Satisfaction Questionnaire for Medication (TSQM, version II)
- Haemophilia - Device Assessment Tool (H-DAT)
- Injection Site Reaction Questionnaire (ISRQ) domain of SIAQ (SIAQ-ISRQ)

VERITAS-Pro[®] or VERITAS-PRN[®], SF-36v2, SDS, TSQM, H-DAT and SIAQ-ISRQ will be scored according to their respective scoring algorithms. Change after 24 weeks from treatment onset and after 76 weeks from treatment onset will be described.

Statistical Analysis Plan
 Trial ID: NN7415-4255
 UTN: U1111-1179-3872
 EudraCT No.: 2016-000614-29

~~CONFIDENTIAL~~

Date:
 Version:
 Status:
 Page:

13 July 2018
 1.0
 Final
 12 of 14

Novo Nordisk

2.4.5.3 Exploratory pharmacokinetic and pharmacodynamic endpoints

- Concentration of concizumab over time during 24 hours PK assessment
- Concentration of free TFPI over time during 24 hours PD assessment
- Thrombin generation over time during 24 hours PD assessment
 - Peak of thrombin generation time during 24 hours PD assessment
 - ETP time during 24 hours PD assessment
 - Velocity index time during 24 hours PD assessment

Individual "concentration over time" curves will be presented in a plot. A mean plot including error bars will also be presented. For thrombin generation the endpoints will be summarized and listed.

2.5 Interim analysis

The trial does not include a formal interim analysis. However, the split of the trial into a main and extension part offers the opportunity of reporting results before the end of the trial. Other reporting of the trial might be done during the extension part once the data collection and review of the main part data has been finalised and individual clinical study reports might in such case be issued. A final clinical study report describing results from the main and extension part will be written when the last patient has either completed or withdrawn from the trial.

All main conclusions regarding clinical proof of concept and dose guidance for phase 3 will be based on the reporting after the main part, see [Figure 2-1](#).

[figure not shown]

Figure 2-1 Definition of main and extension part

Statistical Analysis Plan
Trial ID: NN7415-4255
UTN: U1111-1179-3872
EudraCT No.: 2016-000614-29

~~CONFIDENTIAL~~

Date: 13 July 2018
Version: 1.0
Status: Final
Page: 13 of 14

Novo Nordisk

3 Changes to the statistical analyses planned in the protocol

As described in section 1.2 of this document, the scope of this SAP is to specify some further technical details on matters which have not been adequately described in the protocol. No changes have been made to the analyses specified in the protocol.

3.1 Clarification of bleeding episodes for primary endpoint

Section 17.3 of the protocol defines the primary endpoint as the number of bleeding episodes during at least 24 weeks from treatment onset. As specified in section 2.3 of this document, the bleeding episodes considered for the primary endpoint also includes bleeding episodes recorded as post-surgical or caused by surgery or other medical or dental procedures.

3.2 Offset definition for negative binomial regression for primary endpoint

Section 17.3 of the protocol defines the offset of the negative binomial regression as log of exposure time in the main period. This definition only accounts for the second CPoC criterion. The offset should reflect the observation period which differs for the first CPoC which has been further clarified in section 2.3 of this document. This clarification is in line with the beginning of section 17 as described below.

Section 17 of the protocol describes that the CPoC will be evaluated in a hierarchical fashion using two criteria to evaluate the effect of concizumab. The first CPoC criterion is evaluated using only a subset of observations where concizumab patients are at the last dose level reached at the time of analysis and excluding observations from the 2 weeks run-in period with 0.15 mg/kg. The second CPoC criterion is evaluated using all observations in the main part.

The offset for first CPoC criterion is the log of the individual exposure time at the last dose level reached at the time of analysis excluding the 2 weeks run-in period for subjects on 0.15 mg/kg. The offset for the second criterion is the log of the individual exposure time in the main part.

